9.2.2 Subject/Patient/Healthcare Professional Eligibility

9.2.2.1 Inclusion/Exclusion Criteria

Inclusion criteria

HD patients in AROii cohort i) aged ≥ 18 , ii) filled a cinacalcet prescription after 01 January 2007, iii) enrolled in AROii for at least 90 days prior to cinacalcet initiation and have at least 90 days follow-up following cinacalcet initiation (*Cohort A*). HD patients who have serum Ca ≥ 8.4 mg/dL at time of cinacalcet initiation will be included in subsequent analyses (*Cohort B*). A sub-set of HD patients who develop hypocalcemia (serum Ca < 8.4 mg/dL) will define *Cohort 1* which will be used to evaluate the primary objectives. HD patients with hypocalcemia who discontinued cinacalcet will be included in further sub-analyses (*Cohort C*).

Exclusion criteria

Patients with i) parathyroidectomy up to and including the first 90 days of follow-up, ii) a prescription for cinacalcet is less than 15 days (2 weeks) with no further prescriptions

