9.3.3 Covariate Assessment

Table 2 summarises the covariates to be evaluated. The most proximal values identified at the end of the baseline period will be used in the analysis. Time-varying covariates will be evaluated at consecutive 90 days intervals following the baseline period. Continuous (e.g. laboratory parameters, age, BMI, systolic blood pressure and etc) time varying covariates will be determined at the end of each interval (one value only). Categorical (e.g. concomitant medications, medical events etc) time-varying covariates will be determined by the occurrence of a prescription or event respectively within an interval. During intervals where an event of interest occurs, only data prior to the event will be used in the corresponding time-varying analysis (most recent value prior to the event for continuous covariates and vascular access). The presence (combined therapy) or absence of alternative therapeutic class (AVD for the cinacalcet-related analysis; cinacalcet for the AVD-related analysis) will be integrated as a covariate. For the exposure period pre-KDIGO covariate if the baseline period or the interval corresponding to the time-varying analysis included the date of the publication of the KDIGO guidelines, then the value of this covariate will be set to Yes.

Table 2: Baseline and time-varying covariates

Parameter type	Covariate	Categories	Variable type in time-varying analysis
Demographics	Age	<30, 30-49, 50-64, 65+	baseline
	Gender	Male/female	baseline
	Country		baseline
	Exposure period pre-KDIGO*	Yes/No	time-varying
	Mean time of follow-up following cinacalcet initiation		
Clinical	Hospitalisation	Yes/No	time-varying
	BMI	<18.5, 18.5-<25, 25-<30, ≥30	baseline
	Pre-dialysis systolic blood pressure [mm Hg]	<120; 120-<130; 130-<140; 140-<160; 160+	time-varying
	Smoking status	Current, Former, Non-smoker	baseline
Medical history	CKD aetiology	Hypertension / vascular, Glomerulonephritis, Diabetes, Tubulo-interstitial, Polycystic Kidney Disease, Invalid/Missing, Unknown	baseline
Medical events	Diabetes	Yes/No	baseline
	Cancer	Yes/No	baseline
	CVD	Yes/No	time-varying
	Fracture	Yes/No	time-varying
Dialysis parameters	Vascular access	Catheter vascular access only, Non-catheter vascular access only, Missing	baseline
	Dialysis vintage	Continuous	time-varying
	Calcium dialysate concentration [mEq/L]	<2.5, ≥2.5	time-varying
	Net Ultrafiltration [L]	Quartiles	baseline
	Actual blood flow [mL/min] *	Quartiles	baseline

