Laboratory parameters	Hemoglobin [g/dL]	<10, 10-<12, ≥12	baseline
	Ferritin [µg/L]	<500, ≥500	baseline
	CRP [mg/L] *	Quartiles	baseline
	Serum albumin [g/L] *	Quartiles	time-varying
	Creatinine [µmol/L] *	Quartiles	baseline
	Total calcium [mmol/L]	<2.10, 2.10-2.37, >2.37	time-varying
	Phosphate [mmol/L]	<1.13, 1.13-1.78, >1.78	time-varying
	Alkaline phosphatase	<44 IU/mL, 44-147 IU/mL (normal), >147	time-varying

	PTH [pg/mL]	<150, 150-<300, 300-<600, ≥600	time-varying
Medication use	Cinacalcet use [§]	Yes/No	time-varying
	Paricalcitol use [§]	Yes/No	time-varying
	Older AVD use [§]	None; Alfacalcidol; Calcitriol; both	time-varying
	Phosphate binder use [§]	None, Only calcium-based, Only non calcium-based, Any	time-varying
	Cardiovascular medication [§]	Yes/No	time-varying

01 August 2009. If the baseline period or the interval corresponding to the time-varying analysis includes the publication of the KDIGO guidelines, then the value of the value of exposure period pre-KDIGO covariate will be set to Yes; [§] relevant ATC codes in Appendix B; ^{} The quartiles' cut-offs for these variables will be derived at baseline.

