9.6.2.2 Analysis of the Primary, Secondary and Exploratory Endpoint(s)

9.6.2.3 Primary and secondary objective endpoints

Point estimates and 95% confidence intervals will be derived to determine the rate of hypocalcemia following cinacalcet initiation, rate of cinacalcet discontinuation following hypocalcemia event and rate of cinacalcet re-initiation following discontinuation due to hypocalcemia.

Time to first hypocalcemia event, time to any treatment intervention following hypocalcemia event, and time to cinacalcet re-initiation will be estimated using Kaplan-Meier methods according to baseline calcium levels (i.e. mild, moderate or severe) at baseline.

Cox regression models will be used to identify baseline covariates (Table 2) associated with time to first occurrence of hypocalcemia during the first 12 months of the study, time to any treatment intervention during the 12 months following hypocalcemia event and time to cinacalcet re-initiation during the 12 months following cinacalcet discontinuation. Subjects who do not experience hypocalcemia will be censored (according to 9.2.4.1 criteria). Univariate analysis will be performed. Variables significant at the 0.25 level in univariate analysis will be entered into a multivariate analysis using a stepwise regression technique (significance levels of 0.10 for inclusion/exclusion). Hazard ratios and 95% confidence intervals will be presented.

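### Table 2's calcium bands collapse in the Cox models: to a single split in Cohort B and, if the hypocalcemic value is the baseline, to almost a constant in Cohort 1

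*Protocol*

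**What the plan says.** Table 2 in Section 9.3.3 has a column of categories. Age, for example, is "<30, 30-49, 50-64, 65" (the last band open upwards), PTH is "<150, 150-<300, 300-<600, ≥600" and total calcium in mmol/L is "<2.10, 2.10-2.37, >2.37". Net ultrafiltration, blood flow, CRP, albumin and creatinine are in quartiles, with the note "The quartiles' cut-offs for these variables will be derived at baseline". Dialysis vintage is the one covariate marked as continuous.

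Section 9.6.2.3 then states: "Cox regression models will be used to identify baseline covariates (Table 2) associated with time to first occurrence of hypocalcemia". The same models serve time to any treatment intervention and time to re-initiation. Selection follows: "Variables significant at the 0.25 level in univariate analysis will be entered into a multivariate analysis using a stepwise regression technique", with "significance levels of 0.10 for inclusion/exclusion".

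Two other rules bear on calcium. Section 9.2.2.1 defines Cohort B by "serum Ca ≥ 8.4 mg/dL at time of cinacalcet initiation will be included in subsequent analyses". Section 9.3.3 uses the value closest to the end of the baseline period, and under Section 9.2.3 the baseline period of Cohort 1 ends when hypocalcemia develops.

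**The concern.** Objectives 8.1.4 and 8.2.5 ask which factors are associated with a change of treatment and with time to hypocalcemia. A banded predictor treats everyone within a band as identical. For most Table 2 variables that loses a modest amount of information. For calcium the bands meet the cohort definitions, which themselves cut on calcium at almost the same point as the lowest band. In Cohort B a patient entering at 8.5 mg/dL and one entering at 9.4 mg/dL are the same in a model of time to falling below 8.4 mg/dL.

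The calcium effect left unmodelled within a band does not vanish. It passes to whatever else in the model is correlated with calcium. Because selection is by p-value, such a factor could be reported as a predictor without having an effect of its own.

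**Working it through.** **The plan's own figure.** Section 9.5: 1,245 × 0.47 = 585, rounded to about 600. Half width = 1.96 × √(0.25/600) = 0.040, and 0.0405 at 585. This reproduces, and nothing below changes it.

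**Bands against cohort limits** (1 mmol/L = 4.008 mg/dL).
- Cohort B entry: 8.4 / 4.008 = 2.096 mmol/L.
- Top of the lowest band: 2.10 × 4.008 = 8.417 mg/dL. Only 8.400-8.417 mg/dL lies both inside Cohort B and inside that band.
- The remaining cut: 2.37 × 4.008 = 9.50 mg/dL.

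The protocol gives no calcium distribution. Assume a normal one with mean 2.35 and SD 0.18 mmol/L, truncated at entry. The share in the lowest band is [Φ((2.10 − 2.35)/0.18) − Φ((2.096 − 2.35)/0.18)] / [1 − Φ((2.096 − 2.35)/0.18)] = (0.0824 − 0.0790)/0.921, about 0.4%, or some 5 patients in 1,245. Records rounded to 0.1 mg/dL would add those at exactly 8.4.

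**Variance kept by one split at 2.37.** Formula: Σ pₖ(meanₖ − mean)² / variance. For assumed mean and SD of 2.25 and 0.15, 2.35 and 0.18, and 2.45 and 0.18, the results are 62%, 66% and 57%. Quartiles of a normal variable keep 86%.

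**Effect on selection in Cohort B.** Simulated Cox models used n = 1,245, 47% events and 1,000 runs per cell. Calcium has a true log-linear effect. A second factor has none but is correlated with calcium, and is tested at 0.10. The effects, correlations and calcium distribution (2.35, 0.18, cut at 2.10) are assumptions. Percent of runs in which the second factor is selected:

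| HR per SD lower calcium | Correlation | Calcium split at 2.37 | Split, second factor in quartiles | Calcium as spline (4 knots) |
|---|---|---|---|---|
| 1.25 | 0 | 8.4 | 8.8 | 8.8 |
| 1.25 | 0.3 | 14.0 | 12.4 | 9.1 |
| 1.25 | 0.5 | 24.3 | 16.8 | 9.3 |
| 1.54 | 0 | 10.4 | 9.6 | 11.8 |
| 1.54 | 0.3 | 26.5 | 18.8 | 11.6 |
| 1.54 | 0.5 | 48.7 | 32.9 | 10.2 |
| 2.0 | 0 | 10.6 | 10.4 | 11.2 |
| 2.0 | 0.3 | 40.7 | 26.0 | 9.3 |
| 2.0 | 0.5 | 81.0 | 56.0 | 9.9 |

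The Monte Carlo standard error is at most √(0.25/1000) = 0.016. Some fits overflowed and were counted as not selected, so a few rates may be slightly low. A separate simulation (n = 1,100, HR 1.5-2.0, correlation 0.3-0.5) gave the no-effect factor an HR of 0.96 to 0.86 with 95% interval coverage of 90% down to 69%. With continuous calcium these were 1.00-1.01 and 93-96%.

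**A quartile variable in place of calcium.** Selection was 10-17% at correlation 0.3 and 13-34% at 0.5. With the second factor also in quartiles it was 11-12% and 11-20%.

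**Cohort 1.** Every value defining the event is below 8.4 mg/dL = 2.096 mmol/L, hence in the <2.10 band. If that value is the baseline, the calcium covariate hardly varies. If the last value before the event is meant, it is at least 8.4 mg/dL and the Cohort B collapse returns. Section 9.6.2.3 describes baseline calcium as mild, moderate or severe, which points to the first reading for this cohort. Section 7.1 cites a US study in which intervention rose with severity (48.6%, 52.2%, 63.5%), so the information lost may matter.

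**The case against.** **Functional form may belong to the SAP.** Section 9.3.3 calls laboratory values, age, BMI and blood pressure continuous, and Section 9.6.2.3 states no functional form. That is fair, and banded entry is a reading. It is the natural one: Table 2 gives categories for every measured covariate but one, marks that one as continuous, and is the table named for the Cox models. If continuous entry is intended, one sentence settles it.

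**The bands have a use.** The calcium, phosphate and PTH cuts match, apart from boundary signs, the control levels of Table 3, give readable hazard ratios and allow non-linearity. This stands for description. It does not help where a band is nearly empty or holds everyone.

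**Severity strata.** Section 9.6.2.6 stratifies the primary and secondary analyses by hypocalcemia severity, which partly offsets the loss in Cohort 1. It does not repair the Table 2 covariate.

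**Stronger readings that the documents do not support.** A reader might infer that banding makes any unrelated factor look predictive; at zero correlation there is no inflation. A reader might extend the bias to every covariate and objective. Quartile variables are affected much less, and no bias was simulated for objective 8.1.4. For objective 8.2.8, samples of 102 and 132 (17% and 22% of 600, discontinuation figures taken from Sections 7.2 and 7.1) showed 10-12% with a quartile predictor. A reader might also take the quartile cut-offs to differ between cohorts. The text does not say so, and the note may only mean that cut-offs are not recomputed at each interval. Nor does banding always cost more parameters: a three-knot spline uses two, as many as three bands and more than two.

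**Conclusion.** The point holds for calcium. In Cohort B the collapse to one split follows from the protocol's own limits and needs only the small assumption that few patients enter between 8.400 and 8.417 mg/dL. In Cohort 1 the loss of nearly all variation is conditional on the hypocalcemic value being the baseline.

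The consequence for selection rests on assumed effects and correlations. With HR 1.25-2.0 per SD and correlation 0.3-0.5, a factor without its own effect is selected in 14-81% of Cohort B models, or 12-56% if that factor is itself in quartiles, against a nominal 10%. The size of Cohort B is also assumed: 1,245 is the protocol's count of all cinacalcet patients, before eligibility. For other measured covariates, continuous entry is better practice with a smaller gain. The discontinuation proportion and its precision are untouched.

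**What to change.** In Sections 9.3.3 and 9.6.2.3, state that baseline calcium enters the Cox models as a continuous term, linear or as a restricted cubic spline with three knots. Treat other measured covariates likewise where the sample allows, with PTH, CRP and ferritin on the log scale. Keep the Table 2 bands for descriptive tables. Report hazard ratios for fixed contrasts, the same in every cohort. Say whether the Cohort 1 baseline calcium is the hypocalcemic value or the last one before it.

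The cost is model coding and table layout on data already held. Presentation is slightly less direct, since a spline needs a plot or chosen contrasts. In Cohort B a three-knot spline for calcium takes one parameter more than the effective single split.

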9.3.4 Validity and Reliability

Extensive procedures have been taken to ensure the analysis dataset contains prescriptions with correct ATC codes, dosage, start and end date, quantity, and route. The process and the QC procedure have validated more than 99.9% of all prescriptions. Validation of other aspects of EuCliD database has been discussed elsewhere (Anker *et al*, 2016; de Francisco *et al*, 2016; Eckardt *et al*, 2015; Floege *et al*, 2015; Gillespie *et al*, 2015; Stenvinkel *et al*, 2016).

9.4 Data Sources

An extensive medical record for each haemodialysis patient, essential to their clinical care and encompassing general information, past medical history, physiological anamnesis, comorbidities, allergies, amputations, transfusion history, current medication, laboratory tests, vaccination status, residual renal function, dialysis access, surgery (including parathyroidectomy) and transplantation, is captured directly in the EuCliD system on admission to an FMC facility. These data are reflected in AROii.

Demographic and clinical characteristics include age, gender, height, weight, mobility, marital status, education level, occupational status, smoking history, CKD etiology (coded according to ICD-10) and RRT initiation (country, center, modality and date). Detailed records on patient medical history were used to confirm history of cardiovascular disease, cerebrovascular disease, malignancy and diabetes. Information captured on HD therapy includes dialysis vintage, vascular access type and duration of placement, number of treatments per week, duration of treatment, actual blood flow, dialysis adequacy (Kt/V) as well as pre- and post-dialysis weight. Hospitalization data

including admission and discharge dates and ICD-10 codes, and death data, are routinely captured by all FMC sites.

Descriptive information on prescribed medications includes product (description and ATC code), start and end dates of prescription, dose and administration route. Laboratory data, including markers for anaemia, bone and mineral metabolism, inflammation and nutrition, reflects normal clinical care in terms of testing frequency. Specific to this study, calcium and phosphorous are typically tested on a monthly basis, whilst PTH is tested quarterly.

9.5 Study Size

Since this is a study with descriptive objectives, sample size calculations are based on the level of precision (i.e. half width) of the 95% confidence interval (CI) around the point estimate of the proportion discontinuing cinacalcet (p) following development of hypocalcemia. Based on previous analysis by de Francisco et al (de Francisco *et al*, 2016), approximately 1245 HD patients in AROii were prescribed cinacalcet. Based on observational data (Brunelli *et al*, 2015), approximately 47% of patients on cinacalcet are expected to develop hypocalcaemia, so *Cohort 1* is expected to contain approximately 600 patients. The maximum half width of the 95% confidence interval for a proportion based on 600 patients is 0.040.

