9.2 Setting and Study Population

The source population for this study is the AROii cohort, which comprises of adult subjects presenting at one of 304 participating facilities in 14 European countries (*Czech Republic, France, Hungary, Ireland, Italy, Poland, Portugal, Romania, Russia, Serbia, Slovak Republic, Slovenia, Spain, and United Kingdom*) and Turkey enrolled between 01 January 2007 and 31 December 2009. Out of 10,600 patients enrolled, 1876 patients were still on follow-up by the end of 2014.

AROii, a closed-cohort by design, comprises of chronic (ten or more contiguous dialysis sessions) incident (<183 days since commencing renal replacement therapy (RRT)) haemodialysis patients with no history of renal transplantation or peritoneal dialysis. Data are captured electronically via the FMC European Clinical Database (EuCliD) and supplied on a quarterly basis. By Q4 2014, the AROii study population had accrued over 33,000 person-years of follow-up.

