9.8.3 Analysis Limitations

A limitation of this study is that the EuClID prescription module does not request clinicians to enter the exact reasons for initiating, discontinuing or reinitiating cinacalcet prescription or the decision-making process for how to manage hypocalcemia. The data limitation also applies to known side effects of cinacalcet, such as vomiting and nausea which are not accompanied by ICD-10 coding. Therefore, we are unable to assess clinician's perceptions in initiating, discontinuing or reinitiating cinacalcet treatment or the impact of vomiting or nausea alongside hypocalcemia on persistence. The study will rely on recorded information such as laboratory values and coded clinical events to characterize reasons for initiation, discontinuation and reinitiation of cinacalcet treatment following a hypocalcemia event.

Potential delayed use of cinacalcet may have occurred when KDIGO 2009 guidelines was introduced. For each of these cohorts, patients may initiate the treatment in various years between 2007 and 2014 and the lengths between initiation of HD and cinacalcet may be very different between cohorts. Therefore, different prescribing and management patterns may have occurred in hypocalcemia patients who started cinacalcet pre-KDIGO (2007/8/9) and post-KDIGO (2010-2014). We will look at pre- and post-2009 KDIGO time periods to assess whether there are any differences in prescribing and management patterns.

There are also practical difficulties in analyzing physician prescribing patterns. The information of prescribing clinicians are not recorded in the database. In addition, amongst the 304 FMC facilities contributing to AROii, there are on average 3 to 4

physicians attending each facility and they share the responsibility of routine adaption of prescriptions. If information of prescribing physicians were available, we would have a similar ratio of physicians to patients which would make it statistically impossible to study the prescribing patterns amongst physicians.

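### The 0.040 precision figure holds only if patients are independent, yet they are grouped in 304 facilities with shared prescribing, and no facility-clustered variance is named

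*Protocol*

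**What the plan says.** Protocol 9.5 bases the study size on the precision of the estimated proportion who discontinue cinacalcet after hypocalcemia. It starts from the statement that "approximately 1245 HD patients in AROii were prescribed cinacalcet", expects that "approximately 47% of patients on cinacalcet are expected to develop hypocalcaemia", and concludes that Cohort 1 "is expected to contain approximately 600 patients". From this follows: "The maximum half width of the 95% confidence interval for a proportion based on 600 patients is 0.040". The abstract repeats the figure.

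On the structure of the data, 9.2 says that the AROii cohort "comprises of adult subjects presenting at one of 304 participating facilities in 14 European countries" and Turkey. Section 9.8.3 says that each facility has on average 3 to 4 "physicians attending each facility and they share the responsibility of routine adaption of prescriptions", and that the database does not record who prescribed.

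On the analysis, 9.6.2.3 plans point estimates with 95% confidence intervals for the hypocalcemia, discontinuation and re-initiation rates, Kaplan-Meier estimates, and regression: "Cox regression models will be used to identify baseline covariates (Table 2) associated with time to first occurrence of hypocalcemia", and likewise for time to treatment intervention and time to re-initiation. Variables are screened at 0.25 and then selected stepwise at 0.10. Section 9.6.2.4 adds intervals for the exploratory rates. Neither section says how variances are computed. Table 2 lists country but not facility, and 9.6.2.5 repeats the primary analyses by region. The limitations in 9.8 do not mention clustering.

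**The concern.** Discontinuation, treatment change and re-initiation are largely decisions by prescribers. If a small team makes those decisions for all patients of a facility, two patients of the same facility are likely to be more alike than two patients of different facilities. A cohort of 600 then carries less information than 600 independent patients. Section 9.8.3 treats shared prescribing only as an obstacle to studying individual physicians and does not carry it into the precision.

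Section 7.3 says that no formal hypothesis is tested. The conclusions therefore rest on the interval estimates and hazard ratios, and on the honesty of their stated uncertainty. Understated standard errors would also affect which covariates pass the 0.25 and 0.10 thresholds.

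**Working it through.** **Inputs from the protocol.** 1245 cinacalcet patients, 47% expected with hypocalcemia, Cohort 1 of about 600, half-width 0.040 (9.5). 304 facilities (9.2). Discontinuation of about 17% in a cited US observational study (7.2).

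**Inputs that are assumptions.** The ICC (0.05, range 0.01 to 0.20), the number of facilities that contribute Cohort 1 patients (304, 150 or 100), and the coefficient of variation (CV) of patients per facility (0 or 1). The documents give none of these.

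**Reproducing the plan's figures.** 1245 × 0.47 = 585, close to the rounded 600. Half-width = 1.96 × √(p(1−p)/n). With p = 0.5 and n = 600 this is 1.96 × √(0.25/600) = 0.0400. The stated figure is reproduced exactly, with no design effect.

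**Adding clustering.** Design effect DE = 1 + (m(1 + CV²) − 1) × ICC, with m = 600 / number of facilities. The half-width becomes 0.0400 × √DE. An ordinary 95% interval then covers about 2Φ(1.96/√DE) − 1.

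For 304 equal facilities at ICC 0.05: m = 600/304 = 1.97, DE = 1 + 0.97 × 0.05 = 1.05, half-width 0.0400 × √1.05 = 0.041. For 100 facilities with CV 1: m = 6, DE = 1 + (12 − 1) × 0.05 = 1.55, half-width 0.0400 × √1.55 = 0.050.

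| Facilities, CV | ICC | DE | Maximum half-width | Coverage of ordinary 95% interval |
|---|---|---|---|---|
| 304, 0 | 0.01 | 1.01 | 0.040 | 94.9% |
| 304, 0 | 0.05 | 1.05 | 0.041 | 94.4% |
| 304, 0 | 0.20 | 1.19 | 0.044 | 92.7% |
| 304, 1 | 0.01 | 1.03 | 0.041 | 94.7% |
| 304, 1 | 0.05 | 1.15 | 0.043 | 93.3% |
| 304, 1 | 0.20 | 1.59 | 0.050 | 88.0% |
| 150, 1 | 0.05 | 1.35 | 0.046 | 90.8% |
| 100, 1 | 0.05 | 1.55 | 0.050 | 88.5% |
| 100, 1 | 0.20 | 3.20 | 0.072 | 72.7% |

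**Check by simulation.** Beta-binomial outcomes with p = 0.17, n = 600 and ICC 0.05 gave ordinary-interval coverage of about 94% (304 equal facilities), 92% (304, CV 1), 90% (150, CV 1) and 88 to 89% (100, CV 1). This agrees with the formula to within about one percentage point. In the run with 304 facilities and CV 1, only about 202 facilities received any patient, so it does not represent all 304 contributing. A facility-clustered variance gave about 94 to 95% in all four settings.

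**At the cited discontinuation rate.** With p = 0.17 the independent half-width is 1.96 × √(0.17 × 0.83/600) = 0.030. It exceeds 0.040 only when DE is above about 1.77. At DE 1.55 it is 0.030 × √1.55 = 0.037.

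**The case against.** The strongest reply is that the protocol never says its intervals and Cox models assume independence. Section 9.6.2.3 is silent on the variance estimator, a choice that may properly sit in a SAP that is not at hand. This stands. A reader might infer that the plan treats patients as independent throughout, but the documents support that only for the 0.040.

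Second, 0.040 is the worst case at p = 0.5, and at the cited 17% it still bounds the half-width up to a design effect of about 1.77. This also stands. In a closed retrospective cohort with no hypothesis test, no recruitment decision depends on the figure. It is still presented as a maximum, and with any positive ICC and more than one patient in some facilities it is not one.

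Third, with about two Cohort 1 patients per facility and an even spread, little is lost: half a point of coverage at ICC 0.05. That is correct, but an even spread over all 304 facilities is the most favourable case. Section 9.8.1.3 itself says that exposure to the therapies may be unbalanced across countries, which points to uneven counts.

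Fourth, a reader might infer that the Cox analyses would declare false associations at some multiple of 5%. The documents do not support such a figure. The planned procedure has no 5% test but stepwise selection at 0.25 and 0.10. Most Table 2 covariates, such as age, sex, laboratory values and comorbidity, vary within facilities, and for these ignoring clustering need not make intervals too narrow.

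Country as a covariate and the repetition by region deal with differences between countries or regions, not with correlation within a facility.

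**Conclusion.** The point holds in limited form. The 0.040 is arithmetically right but is an independence value presented as a maximum, while the protocol describes the mechanism that would make outcomes within a facility alike. For the intervals and Cox models, the finding is conditional: if they are run in ordinary form, the intervals for prescribing outcomes, and for hazard ratios of covariates constant or nearly constant within a facility, will be somewhat too narrow.

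At an assumed ICC of 0.05, the maximum half-width is about 0.041 to 0.050 and Cohort 1 coverage about 94% to 89%, from 304 equal facilities to 100 facilities with CV 1. At ICC 0.01 with patients spread over all 304 facilities, the effect is negligible. It becomes large only with a high ICC or strong concentration in few facilities. Every size given here depends on those assumptions, which the data could replace.

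**What to change.** In 9.5 and the abstract, say that 0.040 is the half-width under independence, and add the range over assumed ICCs and facility distributions, for example 0.041 to 0.050 at ICC 0.05.

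In 9.6.2.3 and 9.6.2.4, state that intervals for rates and proportions and for Kaplan-Meier estimates use a facility-clustered (sandwich) variance or a bootstrap that resamples facilities. State that the Cox models use a robust variance clustered on facility. Prescriber is not recorded, so facility is the usable cluster. An anonymised facility code should be available: the loss-to-follow-up rule in 9.2.4.1 depends on return to the same or another facility, and 10.2 says that facility information was anonymised. Report the observed facility ICC for discontinuation.

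The cost is a few sentences of protocol or SAP text and one option in the code, with no new data beyond the facility code. The downside is slightly wider intervals and a slightly less favourable stated precision. If the observed ICC is near zero, almost nothing is lost.
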